## Use of Placebo:

**If use of a placebo is planned, provide a justification which addresses the following:**

- a) Describe the safety and efficacy of other available therapies. If there are no other available therapies, state this. As there are no current treatments for COVID-19, there is no other safe or efficacious therapy that we can use instead of placebo.
- b) State the maximum total length of time a participant may receive placebo while on the study.  
14 days.
- c) Address the greatest potential harm that may come to a participant as a result of receiving placebo.  
There should be no harm incurred by participants receiving placebo, which is corn starch (non-resistant digestible starch).
- d) Describe the procedures that are in place to safeguard participants receiving placebo.  
We will perform interim analysis for efficacy to determine if early study termination may be needed if there is evidence of benefit in the intervention arm that precludes us to continue the study ethically.

**4. Continuation of Drug Therapy After Study Closure Not applicable to this project**

**SECTION III: RECRUITMENT/CONSENT AND ASSENT PROCEDURES****1. Targeted Enrollment: Give the number of subjects:**

- a. Targeted for enrollment at Yale for this protocol: 500
- b. If this is a multi-site study, give the total number of subjects targeted across all sites: 1500

**2. Indicate recruitment methods below.** Attach copies of any recruitment materials that will be used.

|  |  |   |
|--|--|---|
|  Flyers                 |  Internet/web postings                       |  Radio                |
|  Posters                           |  Mass email solicitation                     |  Telephone |
|  Letter                            |  Departmental/Center website                 |  Television           |
|  Medical record review* |  Departmental/Center research boards         |  Newspaper            |
|  Departmental/Center newsletters   |  Web-based clinical trial registries         |  Clinicaltrails.gov   |
|  YCCI Recruitment database         |  Social Media (Twitter/Facebook): |   |
|  Other: Testing Sites   |  |   |

\* Requests for medical records should be made through JDAT as described at <http://medicine.yale.edu/ycci/oncore/availableservices/datarequests/datarequests.aspx>

**3. Recruitment Procedures:**

- a. Describe how potential subjects will be identified. Via the use of a Joint Data Analytics Team (JDAT) compiled list of COVID-19 positive patients who are outpatients, we will contact patients via phone calls to ensure inclusion criteria and obtain phone consent. We will also post IRB-approved informational flyers at testing sites and on social media platforms.
- b. Describe how potential subjects are contacted. Mainly via medical record review and phone calls.
- c. Who is recruiting potential subjects? PIs and research assistants via phone.

**4. Assessment of Current Health Provider Relationship for HIPAA Consideration:**

Does the Investigator or any member of the research team have a direct existing clinical relationship with any potential subject?

- Yes, all subjects
- Yes, some of the subjects
- No

If yes, describe the nature of this relationship. The PIs may be involved in the clinical care of the participants if they eventually become hospitalized, but at time of enrollment it is unlikely that any PIs will be involved in the care of the patient.

**5. Request for waiver of HIPAA authorization:** (When requesting a waiver of HIPAA Authorization for either the entire study, or for recruitment purposes only. Note: if you are collecting PHI as part of a phone or email screen, you must request a HIPAA waiver for recruitment purposes.)**Choose one:**

- For entire study
- For recruitment/screening purposes only
- For inclusion of non-English speaking subject if short form is being used and there is no translated HIPAA research authorization form available on the University's HIPAA website at [hipaa.yale.edu](http://hipaa.yale.edu).

- i. Describe why it would be impracticable to obtain the subject's authorization for use/disclosure of this data: To limit contact with COVID-19 positive patients, the only way to request their permission to participate in our study will be via phone calls. To obtain phone numbers and do initial screening to ensure that participants meet the inclusion criteria we will have to access their medical records.

Approaching the patient directly will put the research staff at risk and the community at large as it will promote the spread of this highly infectious virus.

- ii. If requesting a waiver of **signed** authorization, describe why it would be impracticable to obtain the subject's signed authorization for use/disclosure of this data: We will obtain phone consent to commence the study and will ask patients to sign a formal consent form via email if feasible. Bringing the patients to a health care facility to ensure obtaining a signed authorization will put the research staff at risk and the community at large as it will promote the spread of this highly infectious virus.

**The investigator assures that the protected health information for which a Waiver of Authorization has been requested will not be reused or disclosed to any person or entity other than those listed in this application, except as required by law, for authorized oversight of this research study, or as specifically approved for use in another study by an IRB.**

Researchers are reminded that unauthorized disclosures of PHI to individuals outside of the Yale HIPAA-Covered entity must be accounted for in the “accounting for disclosures log”, by subject name, purpose, date, recipients, and a description of information provided. Logs are to be forwarded to the Deputy HIPAA Privacy Officer.

**6. Process of Consent/Accent:** Describe the setting and conditions under which consent/assent will be obtained, including parental permission or surrogate permission and the steps taken to ensure subjects' independent decision-making.

Study team member will explain to each subject (or legally authorized representative) the nature of the study, its purpose, the procedures involved, the expected duration, the potential risks and benefits involved and any discomfort it may entail. Each subject will be informed that participation in the study is voluntary and that he/she may withdraw from the study at any time and that withdrawal of consent will not affect his/her subsequent medical treatment or relationship with the treating physician.

We will contact patients via phone to perform an oral presentation of the study. After presenting the study to patients by phone, an informed consent document will be sent to the patient electronically for subjects to sign digitally. The plan of obtaining informed consent virtually was formulated in order to limit contact with COVID-19 positive patients as the alternative of approaching the patients in person will put the research staff and the community at large at risk as it will promote the spread of this highly infectious virus by bringing these patients to the health system.

No subject can enter the study before his/her informed consent has been obtained.

The informed consent process and form are considered to be part of the protocol, and will be submitted for IRB approval.

**7. Evaluation of Subject(s) Capacity to Provide Informed Consent/Accent:** Indicate how the personnel obtaining consent will assess the potential subject's ability and capacity to consent to the research being proposed.

Every patient will be assessed for capacity by ensuring that they have understanding of the research and are able to repeat back what we discussed in a manner that expresses understanding. Any patients on heavy pain medications will not be eligible for immediate consenting.

**8. Non-English Speaking Subjects:** Explain provisions in place to ensure comprehension for research involving non-English speaking subjects. If enrollment of these subjects is anticipated, translated copies of all consent materials must be submitted for approval prior to use.

We do not anticipate that any non-English speaking subjects will be enrolled.

**Note\*** If more than 2 study participants are enrolled using a short form translated into the same language, then the full consent form should be translated into that language for use the next time a subject speaking that language is to be enrolled.

Several translated short form templates are available on the HRPP website ([yale.edu/hrpp](http://yale.edu/hrpp)) and translated HIPAA Research Authorization Forms are available on the HIPAA website ([hipaa.yale.edu](http://hipaa.yale.edu)). If the translation of the short form is not available on our website, then the translated short form needs to be submitted to the IRB office for approval via modification prior to enrolling the subject. **Please review the guidance and presentation on use of the short form available on the HRPP website.**

**If using a short form without a translated HIPAA Research Authorization Form, please request a HIPAA waiver in the section above.**

**9. Consent Waiver: In certain circumstances, the HIC may grant a waiver of signed consent, or a full waiver of consent, depending on the study.** If you will request either a waiver of consent, or a waiver of signed consent for this study, complete the appropriate section below.

**Not Requesting any consent waivers**

**Requesting a waiver of signed consent:**

- Recruitment/Screening only** (if for recruitment, the questions in the box below will apply to recruitment activities only)
- Entire Study** (Note that an information sheet may be required.)

**For a waiver of signed consent, address the following:**

- Would the signed consent form be the only record linking the subject and the research? YES  NO
- Does a breach of confidentiality constitute the principal risk to subjects? YES  NO

**OR**

- Does the research pose greater than minimal risk? YES  NO
- Does the research include any activities that would require signed consent in a non-research context? YES  NO

**Requesting a waiver of consent:**

- Recruitment/Screening only** (if for recruitment, the questions in the box below will apply to recruitment activities only)
- Entire Study**

**For a full waiver of consent, please address all of the following:**

- Does the research pose greater than minimal risk to subjects?
  - Yes *If you answered yes, stop. A waiver cannot be granted.*
  - No
- Will the waiver adversely affect subjects' rights and welfare? YES  NO
- Why would the research be impracticable to conduct without the waiver? *Write here*
- Where appropriate, how will pertinent information be returned to, or shared with subjects at a later date? *Write here*

#### **SECTION IV: PROTECTION OF RESEARCH SUBJECTS**

**Confidentiality & Security of Data:**

1. What protected health information (medical information along with the HIPAA identifiers) about subjects will be collected and used for the research? We will need subjects' demographics such as age, sex, race, height, weight, and BMI.
2. How will the research data be collected, recorded and stored? We will store all data on the protected/secure/encrypted Yale G drive/server. Other sites will send collected data securely via Yale secure file transfer.
3. How will the digital data be stored? Yale desktop computer.
4. What methods and procedures will be used to safeguard the confidentiality and security of the identifiable study data and the storage media indicated above during and after the subject's participation in the study? All information will be stored on a secured Yale drive. No personal laptops or computers will be used to store any of this information.

All portable devices must contain encryption software, per University Policy 5100. If there is a technical reason a device cannot be encrypted please submit an exception request to the Information Security, Policy and Compliance Office by clicking on url <http://its.yale.edu/egrc> or email [[contact]](mailto:[contact])

5. What will be done with the data when the research is completed? Are there plans to destroy the identifiable data? If yes, describe how, by whom and when identifiers will be destroyed. If no, describe how the data and/or identifiers will be secured.

This information will be kept for five years. After that time it will be destroyed or de-identified, meaning we will replace the identifying information with a code that does not directly identify the participant. The principal investigator (PI) will keep a link that identifies the participant to the coded information, but this link will be kept secure and available only to the PI or selected members of the research team. Any information that can identify the participant will remain confidential. The research team will only give this coded information to others to carry out this research or to investigators approved for use of banked data.

6. If appropriate, has a Certificate of Confidentiality been obtained? NA

#### **SECTION V: POTENTIAL BENEFITS**

**Potential Benefits:** Identify any benefits that may be reasonably expected to result from the research, either to the subject(s) or to society at large. (Payment of subjects is not considered a benefit in this context of the risk benefit assessment.)

If our hypothesis is proven, this simple, minimal risk intervention, will have the potential to reduce healthcare burden and improve the outcomes of COVID-19 positive patients.

#### **SECTION VI: RESEARCH ALTERNATIVES AND ECONOMIC CONSIDERATIONS**

1. **Alternatives:** What other alternatives are available to the study subjects outside of the research? NA, research participation is completely voluntary. As there are no current approved treatments for COVID-19, there are no other standard of care treatments that participants can receive. Participants may change their mind at any time. They are free to choose not to take part in this study. If they begin the study and later change their mind, they can withdraw at any time. Refusing to participate will involve no penalty or loss of benefits to which they are otherwise entitled (such as their health care outside the

study, the payment for their health care and their health care benefits). It will not harm their relationship with their own doctors. If they decide to withdraw from the study, they may withdraw by telling the study staff or sending written notice to the address provided in the consent form.

#### **IMPORTANT REMINDERS**

Will this study have a billable service? **Yes**  **No**

A billable service is defined as any service rendered to a study subject that, if he/she was not on a study, would normally generate a bill from either Yale-New Haven Hospital or Yale Medical Group to the patient or the patient's insurer. The service may or may not be performed by the research staff on your study, but may be provided by professionals within either Yale-New Haven Hospital or Yale Medical Group (examples include x-rays, MRIs, CT scans, specimens sent to central labs, or specimens sent to pathology). Notes: 1. There is no distinction made whether the service is paid for by the subject or their insurance (Standard of Care) or by the study's funding mechanism (Research Sponsored). 2. This generally includes new services or orders placed in EPIC for research subjects.

**If answered, "yes", this study will need to be set up in OnCore, Yale's clinical research management system, for Epic to appropriately route research related charges. Please contact [[contact]](mailto:[contact])**

Are there any procedures involved in this protocol that will be performed at YNHH or one of its affiliated entities? **Yes**  **No**

If you answered "no" to question 4a, or "yes" to question 4b or c, please contact the YNHH Department of Physician Services ([name]) for prior approval before commencing with your research protocol.

#### **IMPORTANT REMINDER ABOUT RESEARCH AT YNHH**

Please note that if this protocol includes Yale-New Haven Hospital patients, including patients at the HRU, the Principal Investigator and any co-investigators who are physicians or mid-level practitioners (includes PAs, APRNs, psychologists and speech pathologists) who may have direct patient contact with patients on YNHH premises must have medical staff appointment and appropriate clinical privileges at YNHH. If you are uncertain whether the study personnel meet the criteria, please telephone the Physician Services Department at [contact]. **By submitting this protocol as a PI, you attest that you and any co-investigator who may have patient contact has a medical staff appointment and appropriate clinical privileges at YNHH.**

**Appendix A: Phone Questionnaire**

**COVID-19 Symptom Severity Questionnaire**

Hello “*Enrolled subject*”

I would like to assess the severity of your COVID-19 symptoms. Please consider the severity of each symptom based on the following scale: absent, mild, moderate, or severe, to the best of your ability. Remember, If you experience severe symptoms, like shortness of breath, at any point during your evaluation for COVID-19, please call 911 to be emergently evaluated by a healthcare provider.

**A. Over the past 2-3 days:**

|  | Absent | Mild | Moderate | Severe |
|--|--------|------|----------|--------|
| 1) Do you have loss of taste or smell?                       |        |      |          |        |
| 2) Do you have any bellyaches, diarrhea, or nausea/vomiting? |        |      |          |        |
| 3) Do you have a cough?                                      |        |      |          |        |
| 4) Are you short of breath or wheezy on rest or exertion?    |        |      |          |        |
| 5) Do you have a fever or feel feverish?                     |        |      |          |        |
| 6) Are you experiencing fatigue?                             |        |      |          |        |
| 7) Do you have a headache?                                   |        |      |          |        |
| 8) Do you have muscle aches, pains, or cramps?               |        |      |          |        |

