**Secondary Outcome Measure:**

TTCR will be defined as a return to normal body temperature to 97°F -99°F as reported by the patient, and resolution of any major presenting symptoms (myalgia, cough, shortness of breath, GI symptoms) maintained for 72 hours.

-To assess the effect of RPS on symptom severity score

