**Secondary Outcome Measure:**

Symptom severity score (2): This will be evaluated using a subjective self-reporting questionnaire (see section 15: Appendices) around eight symptoms, which include:

1) Shortness of breath at rest or on exertion

2) Fatigue

3) Myalgia/ muscle aches

4) Feverishness

5) Cough

6) Headaches

7) GI symptoms

8) Inability to taste or smell

Participants will rate each of their symptoms on an ordinal scale as follows:

absent (0), mild (1), moderate (2), or severe (3). These symptom ratings will be added to define the symptom severity score with a possible score range of 0–24 points.

Inquiry regarding symptom severity score will take place during phone questionnaires with patients performed Q2 days for 14 days from start of treatment then weekly until 30 days from last dose of treatment.

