### **Procedures during treatment and follow up procedures**

*Assessment for primary objective of hospitalization at one month via phone and EHR:*

Every 2 days phone questionnaires (**see attached questionnaire**) and EHR review for the first 14 days followed by once weekly phone call and EHR review to complete a month follow up from last dose of treatment.

*Assessment for secondary objectives of TTCA and symptom severity score via phone and EHR:*

Every 2 day phone questionnaires (**see attached questionnaire**) and EHR review for the first 14 days followed by once weekly phone call and EHR review to complete a month follow up from last dose of treatment.

*Assessment of exploratory objectives*

EHR review to complete 4 months follow up from COVID positive test

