For our secondary outcomes, assuming a TTCA of about 14 days in the placebo group with standard deviation of 5 days, we calculated that a sample size of 196 would be required to provide 80% power (with a two-sided alpha level of 0.05) to detect an absolute reduction in TTCA by 2 days or more in the RPS group. For the outcomes of symptom severity score, we assumed that the placebo group would have a peak score of 20 with a standard deviation of 5 points, and we calculated that a sample size of 32 patients would be required to provide 80% power (with a two-sided alpha level of 0.05) to detect an absolute reduction in symptom severity score of 5 points or more in the RPS group.

Total accrual between all sites is 1500 patients. Depending on accrual rates, some sites may accrue more than other sites with a total goal of 1500 patients.

**Data analysis plan:** The primary outcome of hospital admission rates will be compared with the use of Pearson's chi-square test. The secondary outcomes of TTCA and symptom severity score will be compared in the two groups by means of a two-sample t-test. Adjusted measures and subgroup effects for the primary and secondary outcomes will be analyzed with the use of logistic regression and linear regression, respectively. Generalized estimating equations and linear mixed models will be used to test for an interaction between treatment group and

site in primary and secondary outcomes, respectively. The alpha level will be set at 0.05 for all analyses, 95% confidence intervals will be calculated, and all comparisons will be two-tailed.

*Interim analysis plans:*

Once our enrollment target for the secondary outcomes is reached (n~200), we will perform an interim analysis to assess safety, feasibility and treatment effect.

*Interim analysis 1(safety):*

All adverse events will be summarized and the independent data safety monitoring committee (DSMC) will make recommendations regarding continuation of recruitment. None of the DSMC members will be on our IRB protocol or the study team.

*Interim analysis 2 (feasibility):*

Study enrollment, follow up and any withdrawals from the study will be summarized and discussed by IDSMC to see if the degree of missing data is acceptable and if any further efforts need to be taken to optimize enrollment and follow up. Successful feasibility will be defined as more than 60% of patients took at least 50% of their prescribed doses (as directed by study team).

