**C. Have been taking your starch as instructed? Y/N**

**If No, could you let us know why?**

**D. Have you experienced any side effects from the starch? Y/N**

**If yes, could you tell us about your symptoms?**

**This concludes the questionnaire. You will be contacted every 2 days to review your symptoms. If you have questions regarding your health or diagnosis of COVID-19, please contact your healthcare provider.**

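### The attached phone script does not collect time to clinical recovery as the protocol defines it: no temperature, no dates to bridge the weekly calls, and no dose count for the feasibility criterion

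*Combined protocol and SAP*

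**What the plan says.** The definition is in Section 4, Secondary Outcome Measure: "TTCR will be defined as a return to normal body temperature to 97°F -99°F as reported by the patient", together with resolution of myalgia, cough, shortness of breath and GI symptoms, "maintained for 72 hours". The source is named under Procedures during treatment and follow up: "Assessment for secondary objectives of TTCA and symptom severity score via phone and EHR", using the attached questionnaire. TTCA there and in Section 14 is the same endpoint under another abbreviation. The calls are "performed Q2 days for 14 days from start of treatment then weekly until 30 days from last dose of treatment".

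Appendix A, part A, opens with "Over the past 2-3 days" and rates eight symptoms from absent to severe. Fever is covered by "Do you have a fever or feel feverish". No temperature and no date is requested. The script closes with "You will be contacted every 2 days to review your symptoms" and has no version for the weekly calls. Section 14 sizes the endpoint "to detect an absolute reduction in TTCA by 2 days or more in the RPS group" and compares days by a two-sample t-test. It states neither when the clock starts nor how a recovery between calls is dated.

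On adherence, Drug Information and Treatment Dosage and Administration take compliance from the questionnaire and tell staff to document missed doses at the calls. Sections 13 and 14 define feasibility as more than 60% of patients taking at least half of their prescribed doses. Item C of the script is a Yes/No question with a reason if No.

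**The concern.** An endpoint is what the form records, and here the only form attached does not record what the definition needs. Three things are affected.

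- **Temperature.** A numeric criterion is collected as a graded symptom. A reading outside 97-99°F that the patient does not regard as fever would be counted as recovered.
- **Dating.** The 2-3 day window suits calls every two days but not weekly ones. For recoveries after day 14, the estimated difference in days depends on a rule that the plan leaves open.
- **Doses.** A criterion expressed as a share of prescribed doses cannot be computed for patients who sometimes answer No, because the script never asks how many doses were missed.

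Temperatures and dates that are not asked for at the time cannot be reliably recovered later.

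**Working it through.** **Definition against script**

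| TTCR needs | Appendix A collects |
|---|---|
| Patient-reported temperature, 97-99°F | Fever item graded absent to severe; no reading |
| Four symptoms resolved | All four are asked |
| 72 hours' duration | A 2-3 day window: 72 hours if read as 3 days, not if read as 2 |
| A number of days | No dates |

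Record review does not clearly fill the temperature gap. The definition calls for a patient's report, and follow-up is by phone and record only.

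**The plan's own sample size**

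Inputs from Section 14: difference 2 days, SD 5, two-sided alpha 0.05, power 80%. Per arm, n = 2(1.960 + 0.842)² × 5² / 2² = 2 × 7.85 × 6.25 = 98.1. Two arms give 196, as stated (198 if each arm is rounded up).

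**Weekly gap**

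Unasked days per weekly interval: 7 − 3 = 4 to 7 − 2 = 5. Over the four intervals from day 14 to day 42 that is 16-20 of 28 days. A recovery first confirmed at a weekly call can be placed only within about 4-7 days.

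**How many recoveries are affected**

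The plan gives no time origin, so I assumed the clock starts 0, 3 or 5 days before first dose. With placebo recovery times normal (14, 5), the share falling after treatment day 14 is P(Z > lag/5) = 50%, 27% or 16%.

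**Effect of the missing dating rule**

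Simulation with 2,000,000 patients per arm:

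- Recovery times are normal (14, 5) and (12, 5), floored at 0.
- Calls fall on days 0, 2, …, 14, 21, 28, 35, 42 and 44 from first dose.
- A call confirms recovery if the whole 2- or 3-day window before it is clear.
- The clock starts 0, 3 or 5 days before first dose.

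| Dating rule | Recorded difference (true 2.0 days) |
|---|---|
| Earliest possible date | 1.6-1.8 |
| Interval midpoint | 1.9-2.1 |
| Latest possible date, or call date | 2.3-2.4 |

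**Doses**

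Table 2 gives 3 × 1 + 11 × 2 = 25 doses, or 2, 3, 4, 4, 4, 4 and 4 across the seven two-day intervals. Read Yes as all taken and No as at least one missed. The minimum is the sum of the smallest intervals answered Yes. The maximum is 25 minus the number of No answers. The threshold is 12.5 doses.

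| Yes answers (of 7) | Doses taken |
|---|---|
| 0 | 0-18 |
| 1 | 2-19 |
| 2 | 5-20 |
| 3 | 9-21 |
| 4 | 13-22 |
| 5 | 17-23 |
| 6 | 21-24 |
| 7 | 25 |

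Patients with 0-3 Yes answers straddle the threshold. With 4 or more they clear it (13/25 = 52%), but only if 25 doses stay prescribed. The Toxicities section allows a reduction to once daily. Applied from the fourth interval, this gives 2 + 3 + 4 + 2 + 2 + 2 + 2 = 17 doses, and four Yes answers can then mean 8/17 = 47%.

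The study summary, Study Design and Section 14 describe twice-daily dosing for all 14 days, which gives 28 doses. On that reading, 3 Yes answers span 12-24 around a threshold of 14 and 4 Yes answers give at least 16, so the cutoff is the same but the denominator differs.

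**The case against.** Much can fairly be said for the plan.

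- A reader might infer that the temperature criterion has become pure feeling. It has not: the item asks about fever as well as feverishness, so a fever the patient knows of should be reported. What is lost is readings outside 97-99°F that the patient does not call fever. The documents give no basis for sizing that.
- A reader might infer that an unseen relapse between weekly calls invalidates a recovery. The definition asks for 72 hours only, so a later relapse does not undo it. On a 3-day reading of the window, one clear weekly call already covers the 72 hours. The main loss is dating.
- A reader might infer a false treatment effect or a loss of power. Both arms share one call schedule and are blinded, so coarse dating creates no difference where none exists. At about 675 per arm (1500 less 10%, halved), power stays near 100% under every rule. A midpoint rule is nearly unbiased.
- A reader might infer that the feasibility criterion can never be evaluated. If more than 60% of patients are clearly above half their doses, it is met without classifying anyone else.
- A reader might infer that admissions are missed because the script does not ask. The protocol assigns hospitalization to phone and record review, and Table 4 has a row for it.

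It also stands that staff are told to document missed doses, that treatment deviations must be recorded, and that a case report form and a data-capture system exist but are not shown. They may hold further fields. None is described, however, and Study Design calls the questionnaire pre-specified, so extra questions left to callers could differ between sites.

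**Conclusion.** The mismatch holds for the script as attached. It collects the four TTCR symptoms but not the temperature criterion, and it cannot date recoveries in the weekly phase to better than several days. The missing dating rule alone moves a true 2.0-day difference to anywhere from about 1.6 to 2.4 days. That range rests on the plan's means and SD, and on my assumptions of normal shape and a clock starting 0-5 days before first dose. It is a matter of what is measured and how it is dated. The feasibility criterion can be evaluated only if more than 60% of patients are clearly above 50% of prescribed doses. Otherwise the unclassifiable patients decide it. This touches a secondary endpoint and an interim criterion, not the primary outcome, and it should be corrected.

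**What to change.** In Appendix A add:

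- (a) the patient-reported temperature with its date, and the date of the last reading outside 97-99°F, with a box for no reading available;
- (b) the date each TTCR symptom last occurred since the last call, keeping the 2-3 day grading for the severity score;
- (c) during treatment, the number of doses missed and the number prescribed since the last call.

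Correct the closing line for the weekly calls. In Section 14 state the TTCR time origin, the dating rule (the reported date, otherwise the interval midpoint) and how patients without a temperature reading are handled. Reconcile the once-daily lead-in in Table 2 and Appendix B with the passages describing twice-daily dosing for 14 days, so that the dose denominator is fixed.

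The cost is a short form amendment, slightly longer calls and some recall error in dates over up to seven days. The documents mention delivery of starch and printed instructions only, so some participants may have no thermometer and those readings will be missing. The proposal leaves the sample size and the test unchanged.
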